Pre-diabetes and Type II diabetes involve an impaired post-receptor response to insulin that hinders the glucose uptake response after meal consumption.¹⁷⁻¹⁹ Chronic hyperglycemia and the resulting compensatory hyperinsulinemia promote a cohort of acute and chronic sequelae including cardiovascular disease, liver complications, central nervous system degeneration and hyperglycemic osmotic stress.²⁰⁻²³ Axulin is a natural health product consisting of a mixture of extracts from herbs and vegetables present in normal diets which was identified by screening more than 100,000 compounds and extracts in a patented cell-culture based assay system targeting the IRS proteins. In vitro, Axulin has marked effects on the IRS-2 branch of the insulin signaling cascade to enhance downstream insulin signaling. Axulin has been shown in animal models to increase glucose uptake in peripheral tissues and decrease circulating blood glucose and triglyceride concentrations. Regular supplementation of the diet with Axulin would be expected to reduce the incidence of associated pre-diabetic and diabetic complications, resulting in an increased quality of life for patients without resorting to current anti-diabetic prescription drugs such as metformin and others that may have substantial unwanted side effects in patients.

HYPOTHESES

Axulin will reduce postprandial glucose and insulin responses in a dose-dependent fashion in healthy subjects without diabetes. The reduction in glucose and insulin will be relatively greater in insulin-resistant than insulin-sensitive subjects.

OBJECTIVES

The primary objective of this study is to determine the dose of Axulin which will reduce the incremental area under the blood glucose response curve (AUC) elicited by 75g oral glucose in healthy subjects by $\geq 33\%$.

The secondary objectives are to determine the dose-response effects of Axulin on:

- blood glucose and serum insulin AUC
- % reduction of insulin AUC
- the blood glucose and serum insulin increments at 15, 30, 45, 60, 90 and 120min
- insulinogen index
- Matsuda insulin sensitivity index
- ISSI-2 index of beta-cell function
- incremental blood lipid response at 120min
- plasma triglyceride response
- plasma axulin response

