The primary endpoint is the % reduction in 2-hour incremental AUC for glucose. Using the t-distribution with 2-tailed $p<0.05$ and assuming an average CV of within-individual variation of 2-hour incremental AUC values of 25%, $n=20$ subjects (10 lean and 10 overweight) has 80% power to detect a 17% difference in AUC, 90% power to detect a difference of 19% and 99% power to detect a difference of 26%. Within each subject group ($n=10$) there is 80% power to detect a difference in AUC of 25%, and 80% power to detect a 33% difference between the responses of lean and overweight subjects. To allow for 10% dropout, we will recruit $n=11$ lean and $n=11$ overweight subjects.

Subject Recruitment

Participants will be recruited from the pool of participants at GI Laboratories who have indicated that they are willing to be contacted and asked if they wish to participate in new studies. If an insufficient number of subjects can be recruited, then a newspaper advertisement will be used to recruit new subjects.

Selection of participants

Participants willing to be considered will be invited to come to the research centre to have the study procedures explained to them and be given a copy of the consent form which they may either sign then, take away to sign at a later date, or decline to participate. Participants will be encouraged to ask any questions they may have and not to sign the consent form until all of their questions have been answered to their satisfaction. Those who consent to participate will come to the research centre for a pre-selection visit when subject eligibility will be determined. During this visit, the 10-14hr overnight fasted participants will complete a questionnaire (Appendix 1) to assess medical history, and lifestyle factors, have height, weight, waist circumference and blood pressure measured, and have a blood sample drawn for measurement of glucose, HbA1c, lipids, creatinine, AST, ALT and complete blood count. Females will have a pregnancy test.

PROCEDURES

The study will have a randomized block design with repeated measures. One block, which will be double-blinded, will test the effect of Axulin capsules; the other block, which will be open label, will test the effect of Axulin tablets. Within each participant, the order of the blocks will be randomized and within each block the order of the treatments will be randomized.

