Eligible participants will be instructed to maintain stable dietary and exercise habits and for the duration of the study, to avoid vigorous physical activity for 24hr before each visit and to and consume their normal dinner the night before each visit. At each visit current use of medications and natural health products participants will be reviewed with each participant and any changes will be discussed with the investigator. Female participants will be advised that if they become pregnant during the study they are to contact the investigators and discontinue their participation immediately.

Each subject will be studied on 6 separate days with at least a 3-day interval between tests. On each test day, subjects will come to GI Labs ([name]) in the morning after a 10-14h overnight fast. On each test occasion the subject will be weighed, and give fasting finger-prick and venous blood samples. Blood from a forearm vein will be collected into a 6ml EDTA tube (Vacutainer, BD Canada, Mississauga, ON). Finger-prick blood samples will be collected into 2 separate vials: one (2-3 drops blood into a fluoro-oxalate tube) for glucose analysis and the other (6-8 drops of blood into an 0.3ml Microvette with clot activator, Sarsted, Germany) for insulin. After the fasting sample the subject will take 12 capsules or 2 tablets with a drink of 250ml water. Subjects will rest for 3-10min and have their blood pressure measured; 40min after swallowing the first capsule or tablet a finger-prick blood sample (2-3 drops for glucose and 6-8 drops for insulin analysis) will be collected and then subjects will consume 82.5g dextrose (containing 75g anhydrous glucose) dissolved in 300ml water within 5min plus a drink of 150ml water within 10min of starting the glucose drink. Further finger-prick blood samples for glucose (2-3 drops) and insulin (6-8 drops) will be obtained at 15, 30, 45, 60, 90 and 120 min after starting to drink the glucose solution. Venous blood samples (7ml) will be collected after the 60 and 120 min finger-prick. During the test subjects will remain seated quietly except for trips to the washroom if necessary. After the last blood sample subjects will be offered a snack and be free to leave.

Treatments

The 6 treatments administered will consist of the following:

- 12 placebo capsules with 250ml water (0g Axulin)
- 250ml water alone (0g Axulin)

- 4 placebo and 8 Axulin capsules (2g Axulin)
- 16 Axulin capsules (4g Axulin)

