24	Overweight	A	C	B	F	E	D
25	Overweight	B	C	A	E	F	D
26	Overweight	C	A	B	D	F	E

27	Overweight	B	C	A	F	D	E
28	Overweight	D	F	E	B	A	C
29	Overweight	D	E	F	C	B	A
30	Overweight	F	E	D	A	B	C
31	Overweight	A	C	B	E	F	D
32	Overweight	E	D	F	C	A	B

Instructions: please assign capsules to codes A, B or C, and tablets or empty bag to codes D, E or F. Place treatment assignments into a sealed opaque envelope and keep the envelope in an accessible location. Treatments are as follows:

BLOCK 1 (A, B or C)

- Placebo 1; 16 Placebo capsules
- 2g Axulin caps: 4 Placebo capsules plus 8 Axulin capsules
- 4g Axulin caps: 16 Axulin capsules

BLOCK 2 (D, E or F)

- empty bag
- 2g Axulin tablets: 2 Axulin tablets
- 4g Axulin tablets: 4 Axulin tablets

Biochemical Analysis

Finger-prick blood samples for glucose analysis will be placed in the refrigerator immediately after being obtained and at the end of the test placed in a -20°C freezer until analysis which will be performed within 5 days. Glucose analysis is done using an YSI model 2300 STAT analyzer (Yellow Springs, OH). The microvette tubes used to collect blood for insulin analysis will be centrifuged at 3622×g for 2 min and the serum transferred to labeled polypropylene tubes and stored at -20°C prior to analysis of insulin using the Human Insulin EIA Kit (Alpco Diagnostics). Venous blood samples will be stored at 4°C until the end of the study after which they will be centrifuged at ~1400×g for 10 min and the plasma removed and separated into 2×1ml aliquots; 1 for analysis of triglycerides at St. Michael's Hospital biochemistry laboratory and the other for measurement of the active ingredient in Axulin by liquid chromatography/mass spectrometry.

Statistical Analysis

Incremental areas under the blood glucose, insulin and triglyceride response curves (AUC), ignoring area below fasting, will be calculated. Blood glucose and insulin concentrations and AUC values will be analyzed using repeated measures ANOVA examining for the main effects of dose, form (tablets vs capsules) and subject group (lean vs overweight) and their interactions. After demonstration of significant heterogeneity, differences between individual means will be assessed using Tukey's test to adjust for multiple comparisons.

Informed Consent

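### As written, venous blood is held unseparated at 4°C until the study ends, with no stability data, which puts the plasma triglyceride and plasma Axulin endpoints at risk

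*Combined protocol and SAP*

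**What the plan says.** The Biochemical Analysis section states of the venous tubes: "Venous blood samples will be stored at 4°C until the end of the study after which they will be centrifuged". The plasma is then split into two 1 ml aliquots, one for triglycerides at a hospital laboratory and one for the Axulin active ingredient by liquid chromatography/mass spectrometry.

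The same paragraph treats the finger-prick samples differently. Glucose vials are refrigerated at once and "at the end of the test placed in a -20°C freezer until analysis which will be performed within 5 days". Insulin tubes are centrifuged, with "the serum transferred to labeled polypropylene tubes and stored at -20°C prior to analysis of insulin".

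PROCEDURES sets the sampling: "Each subject will be studied on 6 separate days with at least a 3-day interval between tests". A fasting venous sample goes into an EDTA tube at each visit, and "Venous blood samples (7ml) will be collected after the 60 and 120 min finger-prick". That makes three venous draws per visit. The tube type is stated for the forearm-vein sample and not repeated for the two later draws.

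The OBJECTIVES list "plasma triglyceride response" and "plasma axulin response" as secondary. Statistical Analysis plans an incremental area under the curve for triglycerides.

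**The concern.** Read literally, whole blood stays in contact with cells for days to weeks before plasma is removed. The hold also differs between one participant's visits, because early visits wait longest. If prolonged contact with cells alters either analyte (an assumption; the documents are silent), both endpoints gain an error that depends on visit number and cannot be removed afterwards.

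Two stated aims depend on these tubes. One is whether triglyceride effects differ between lean and overweight participants. The other is whether capsules and tablets act alike. The Treatments section includes tablets because Axulin may become available more slowly in that form, and plasma Axulin is the most direct measure of that.

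**Working it through.** The plan states no storage time, stability limit or assay loss, so there is no figure to reproduce. The check derives the holds that the sentence implies.

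**1. Handling side by side (Biochemical Analysis)**

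| Sample | Separated | Frozen | Time limit |
|---|---|---|---|
| Finger-prick glucose | not stated | at the end of the test | analysed within 5 days |
| Finger-prick insulin | centrifuged, serum transferred | -20°C | none stated |
| Venous blood | after the end of the study | not stated | none stated |

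Only the venous samples wait for the end of the study.

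**2. Minimum hold.** Inputs: 6 visits, at least 3 days apart (PROCEDURES). If the end of the study is taken as the participant's own visit 6:

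hold = (6 − visit) × 3 days = 15, 12, 9, 6, 3, 0 for visits 1 to 6; mean 45 / 6 = 7.5 days.

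These are lower bounds. Wider spacing or staggered enrolment lengthens them; an assumed 7-day spacing gives 5 × 7 = 35 days for visit 1.

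**3. Tubes affected.** Inputs: 3 draws, 6 visits, 20 completers or 22 recruited (Number of subjects).

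- All tubes: 3 × 6 × 20 = 360, or 3 × 6 × 22 = 396.
- Held at least 3 days (visits 1–5): 3 × 5 × 20 = 300, or 330.
- Held at least 9 days (visits 1–3): 3 × 3 × 20 = 180, or 198.

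**4. Balance across treatments (Table 1).** Over all 24 sequences, every code A–F has mean visit position 3.50, so mean hold = (6 − 3.50) × 3 = 7.5 days for each. For the subsets likely to be used, the mean holds in days are:

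| IDs | A | B | C | D | E | F |
|---|---|---|---|---|---|---|
| 1–11 and 21–31 (n=22) | 7.77 | 8.05 | 7.91 | 7.23 | 6.95 | 7.09 |
| 1–10 and 21–30 (n=20) | 7.20 | 7.65 | 7.65 | 7.95 | 7.05 | 7.50 |

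At n=20 both blocks average 7.50 days. At n=22 the capsule block averages 7.91 and the tablet/water block 7.09, a difference of 0.82 days.

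**5. Gap in hold within a participant.** The design states: "Within each participant, the order of the blocks will be randomized and within each block the order of the treatments will be randomized". Capsules therefore occupy visits 1–3 or 4–6, and tablets and water alone occupy the other three.

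- Capsule code versus Block 2 code: visits differ by 1 to 5, on average 3. Gap 3 to 15 days, mean 3 × 3 = 9.0 days. By code pair the mean over Table 1 is 7.5 to 10.25 days. These nine pairs include the water-alone code.
- Two codes in the same block: visits differ by 1, 1 or 2, mean 4/3. Gap 3 to 6 days, mean 4/3 × 3 = 4.0 days.

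**6. Illustration only.** Suppose, as an assumption not in the documents, a proportional loss of r per day. The difference in level between two visits whose holds differ by d days is 1 − (1 − r)^d.

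| r per day | visit 1 vs 6 (d = 15) | mean capsule–tablet gap (d = 9) |
|---|---|---|
| 0% | 0% | 0% |
| 0.5% | 7.2% | 4.4% |
| 1% | 14.0% | 8.6% |
| 2% | 26.1% | 16.6% |

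These are differences within one participant. At group level the capsule–tablet distortion of the mean is roughly r times the difference in mean hold: about zero at n=20, and at n=22 about 0.82 × r = 0.4%, 0.8% and 1.6% for r = 0.5%, 1% and 2%.

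**7. Effect on the triglyceride increment.** A constant shift common to the three tubes of one visit cancels when the fasting value is subtracted. A proportional change does not; it scales the whole increment.

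**The case against.** The strongest reply is that the phrase is a drafting slip. Glucose in the same paragraph follows the order refrigerate, then process at the end of the test, and the authors may have meant the same for venous blood. That is plausible, but nothing in the documents corrects it. The protocol generally uses test for a session and study for the whole trial, and staff who follow the sentence will hold the tubes. The mention of an end-of-study visit under Participant Withdrawal Criteria does not settle it either, since it most naturally means the final visit.

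The second reply is that harm is unproven. This stands: no degradation rate is given, the percentages above are hypothetical, and their range includes zero. The randomisation also protects the group means well.

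Third, the tube counts pool both analytes. Two of the six treatments contain no Axulin and fasting tubes precede dosing. Assuming complete washout, only 2 × 4 × 20 = 160 tubes (176 at n=22) carry an Axulin signal. The plan names no specific analysis of plasma Axulin, and its power statement covers neither analyte. These points limit the consequence but do not justify an unsupported hold.

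**Conclusion.** The concern holds. As written, the handling rule exposes two secondary endpoints to storage of at least 0 to 15 days, varying by visit, with no stability evidence in the text reviewed. That the sentence needs changing or supporting is certain. That the results would be damaged is a risk of unknown size, resting on the assumption that cell contact at 4°C alters triglycerides or the Axulin active ingredient.

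With all 24 sequences used, the main expected harm is extra within-participant variability, greatest for capsule versus tablet. Systematic bias between treatments would be small unless dropout or partial use of Table 1 unbalances visit order. The primary glucose endpoint and all insulin endpoints use finger-prick blood and are not touched. This should be fixed before sampling starts, because it cannot be repaired afterwards.

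**What to change.** If the session was meant, replace the words about the end of the study with *until the end of that test session*. Then centrifuge, aliquot and freeze the plasma for batch analysis. State the storage temperature and the maximum storage time confirmed for each assay, and in particular confirm that frozen plasma suits the LC/MS assay. State the tube type for the 60 and 120 min draws as well.

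If the long hold is intended, give stability data for both analytes covering the longest planned hold, and record draw and centrifugation dates for every tube so that hold can be examined in the analysis.

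The cost is one sentence, plus centrifuging three tubes per session (3 × 6 = 18 per participant) at a site that already centrifuges the insulin tubes. Freezer space is needed for two 1 ml aliquots per tube: 2 × 360 = 720 at n=20, or 2 × 396 = 792 at n=22.

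### Glucose and insulin increments are listed as endpoints, but the plan analyses unadjusted concentrations; the same edit should confirm the pre-dose sample as zero for the glucose and insulin AUCs

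*Combined protocol and SAP*

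**What the plan says.** All places are in the combined protocol and SAP.

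- **Objectives.** The secondary list includes "the blood glucose and serum insulin increments at 15, 30, 45, 60, 90 and 120min".
- **Statistical Analysis.** The variables to be tested are named once: "Blood glucose and insulin concentrations and AUC values will be analyzed using repeated measures ANOVA". The factors are dose, form and subject group, with their interactions. Increments at single time points are not mentioned, and there is no baseline covariate.
- **Statistical Analysis, AUC definition.** "Incremental areas under the blood glucose, insulin and triglyceride response curves (AUC), ignoring area below fasting, will be calculated".
- **Procedures.** Each test day has two finger-pricks before the glucose drink, both for glucose and insulin. The first is called fasting and precedes the product. The second is described only as "40min after swallowing the first capsule or tablet a finger-prick blood sample", and the glucose drink follows it. Later finger-pricks are timed from the start of that drink. Venous blood is drawn at fasting and after the 60 and 120 min finger-pricks, so there is no venous sample at 40 min.
- **Number of subjects.** "The primary endpoint is the % reduction in 2-hour incremental AUC for glucose". The Objectives set the target at a reduction of at least 33%.

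**The concern.** An increment is a concentration minus a reference value from the same visit. Objectives name the increment and the analysis section names the concentration. A statistician who follows the analysis section will test something other than the listed endpoint. Each participant attends six times, and every difference between two treatments at a given time point will include the difference in fasting level between those two mornings, although that level has been measured and could be removed.

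An increment also needs a stated zero, and two pre-glucose samples are available. The second is taken after treatment. If it served as zero, any effect of Axulin in the first 40 min would be subtracted from every later point. The AUC sentence points to the pre-dose sample, but the plan does not say what the 40-min sample is for, and the primary endpoint depends on the same choice.

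**Working it through.** **1. The plan's own figure.** Number of subjects states that n=20 "subjects (10 lean and 10 overweight) has 80% power to detect a 17% difference in AUC", with a within-individual CV of 25% and two-sided 5% significance. Taking 25% as the SD of the paired difference:

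detectable difference = 25/√20 × (t₀.₉₇₅,₁₉ + t₀.₈₀,₁₉) = 5.59 × (2.093 + 0.861) = 16.5%, stated as 17%.

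The figure reproduces, and this point does not change the sample size. The 17% and the 33% target serve below as yardsticks.

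**2. Increments against concentrations.** For one participant and one time point, let C be the concentration, F the visit's pre-dose fasting value and Δ = C − F. Between treatments i and j:

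C_i − C_j = (F_i − F_j) + (Δ_i − Δ_j).

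F is measured before dosing and order is randomised, so F_i − F_j has expectation zero. Both analyses therefore estimate the same mean treatment difference, but the concentration analysis carries F_i − F_j as extra variation.

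Whether subtraction improves precision depends on quantities the documents do not give. With within-subject between-visit SDs s_C and s_F and correlation r, the variance of a two-visit difference is:

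- concentrations: 2s_C²
- increments: 2(s_C² + s_F² − 2r·s_C·s_F), smaller only if r > s_F/(2s_C)
- concentrations with F as covariate: about 2s_C²(1 − r²), not larger apart from the cost of estimating one slope

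No number can be put on the gain. The mismatch with the listed endpoint does not depend on it.

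**3. Which zero for the glucose AUC.** The documents give no concentrations, so this step is an illustration on assumed inputs. If the zero moves by d over a 120-min window and the curve stays above it, the AUC moves by at most 120 × d:

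shift in % reduction ≤ 100 × 120 × d / control AUC.

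| assumed d (mmol/L) | AUC 150 | AUC 200 | AUC 250 | AUC 300 |
|---|---|---|---|---|
| 0.1 | 8.0 | 6.0 | 4.8 | 4.0 |
| 0.2 | 16.0 | 12.0 | 9.6 | 8.0 |

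(AUC in mmol·min/L; entries in percentage points.)

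**4. Check by trapezoid.** The assumed control curve is 5.0, 6.5, 8.2, 8.6, 8.2, 7.0, 6.0 mmol/L at 0, 15, 30, 45, 60, 90, 120 min. Its incremental AUC is 15 × (0.75 + 2.35 + 3.4 + 3.4) + 30 × (2.6 + 1.5) = 148.5 + 123.0 = 271.5.

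- *Post-load increments cut by 33%, 40-min value lower by 0.2.* The reduction is 33.5% from the pre-dose zero and 24.7% from the 40-min zero, a gap of 8.8 points. The bound is 100 × 120 × 0.2/271.5 = 8.8.
- *Whole curve lower by 0.2.* The reduction is 8.8% from the pre-dose zero and 0% from the 40-min zero.
- *Only the 40-min value higher by 0.2.* The 40-min zero shows an apparent reduction of 8.3%, although no post-load value has changed. The direction depends on the sign of the pre-load shift.

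**5. Triglycerides.** There is one pre-glucose venous sample, so the triglyceride AUC has only one possible zero.

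**The case against.** **The AUC reference is already given.** The analysis section cuts area at fasting, and Procedures uses that word on test days only for the pre-product sample. This stands. A reader might infer that the plan leaves the primary endpoint without a baseline, or that it will be biased by a post-dose zero. The documents support neither: on the plain reading the zero is pre-dose, and nothing mentions averaging the two samples. What is missing is the time-0 point and the role of the 40-min sample.

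**The size of the AUC effect is hypothetical.** This also stands. A reader might go further and say that a true 33% reduction would be reported as about 21% (33 − 12, with d = 0.2 and control AUC 200). That takes the upper bound, an assumed shift before any glucose load, and an analyst who departs from the word fasting. The documents contain no human onset or concentration data. The objective also concerns the area elicited by the glucose, which could be argued to favour the sample just before it. That is a reason to state the choice, not evidence of error.

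**Randomised order removes bias from the concentration analysis.** Correct for treatment contrasts, and a single fasting reading brings its own measurement error. The listed endpoint still has no stated analysis.

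**A dose-by-time interaction that included the fasting value would in effect compare increments.** It would, but time is not among the factors listed.

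A reader might also extend the point to the insulinogenic, Matsuda and ISSI-2 indices. The documents name them without formulas, so no effect on them can be shown from the text.

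**Conclusion.** The mismatch is real: increments at six times are listed as a secondary endpoint, and the plan analyses concentrations without baseline adjustment. The consequence is an unanalysed secondary endpoint and avoidable noise in the treatment contrasts, not bias. The amount of noise cannot be derived from the documents.

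For the glucose and insulin AUCs, confirmation is all that is needed. For glucose, the case for writing it down is that the wrong zero could move the primary % reduction by up to about 4-16 points. That range assumes a 0.1-0.2 mmol/L pre-load shift, control AUCs of 150-300 mmol·min/L and a curve that stays above baseline. It is not negligible beside a 33% target and a 17% detectable difference, but it arises only if the analyst leaves the plain wording. Sample size and the triglyceride AUC are unaffected.

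**What to change.** In Statistical Analysis:

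1. Replace concentrations, as the analysed time-point variable, with glucose and insulin increments at 15, 30, 45, 60, 90 and 120 min, each taken from that visit's pre-dose fasting finger-prick. Optionally also report concentrations with the same pre-dose value as covariate. The covariate analysis should accompany the increments rather than replace them, since the increments are the listed endpoint.
2. State, for the glucose and insulin AUCs only, that fasting means the pre-dose finger-prick. State that the 40-min post-dose sample is the time-0 point of the 2-hour curve and not the reference level.
3. Report the glucose and insulin AUCs from the 40-min zero as a sensitivity analysis.
4. Leave the triglyceride AUC as it is, since no 40-min venous sample exists.

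The cost is a few sentences and one sensitivity analysis, with no new samples or visits. The downside is small: increments inherit the measurement error of a single baseline reading. The wording should be settled before the treatment codes are opened.

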The GI Testing protocol has been approved by the Western Institutional Review Board® which meets all requirements of the US Food and Drug Administration (FDA), the Department of Health and Human Services (DHHS), the Canadian Health Protection Branch (HPB), Canadian

Institutes for Health Research (CIHR) and the European Community Guidelines. Informed consent is obtained from all subjects for each series of tests they participate in.

Participant Withdrawal Criteria

The Investigator may elect to withdraw the participant from the study or the participant may withdraw from the study at any time. Reasons for withdrawing include, but are not limited to:

- Development of an exclusion criterion during the course of the study
- Study product never consumed
- Participant was lost to follow-up
- Participant did not follow study procedures
- Participant elected to withdraw from the study for any reason
- Investigator elected to remove participant from the study for any reason
- Subject takes longer than the specified time to complete the study

In the case of premature withdrawal, all planned assessments for the end of the study visit will be completed and the sponsor will be informed as soon as possible. The subject's Case Report Form ("CRF") will be completed including the final assessment. The date and main reason for the premature withdrawal will be clearly documented in the subject's file and written down on the CRF

ADVERSE EVENT REPORTING

An adverse event (AE) is any symptom, injury, illness, or medical/surgical procedure whether planned or not or whether associated with the study foods or not. AEs will be assessed at each visit and recorded in the Case Report Forms. AEs will be evaluated for duration, severity, seriousness, and causal relationship to the food items provided in the study by the study physician who will decide if any action is required and provide referral, treatment, and/or follow-up as appropriate until resolved, judged to no longer be clinically significant, or if a chronic condition, until fully characterized. Research staff will record the final outcome and resolution date of the event wherever possible. The action taken and the outcome will be recorded in the Case Report Form.

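### Low glucose readings are not counted by subject and the adverse event definition omits laboratory values, so a symptom-free low after Axulin would be neither identified as low nor recorded as an adverse event

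*Combined protocol and SAP*

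**What the plan says.** **Mechanism and hypothesis.** The background text says: "In vitro, Axulin has marked effects on the IRS-2 branch of the insulin signaling cascade to enhance downstream insulin signaling". For animal models it reports that Axulin acts to "decrease circulating blood glucose and triglyceride concentrations". The HYPOTHESES section predicts: "Axulin will reduce postprandial glucose and insulin responses in a dose-dependent fashion in healthy subjects without diabetes".

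**Sampling.** Under PROCEDURES, subjects are dosed after an overnight fast. A further sample, "40min after swallowing the first capsule or tablet a finger-prick blood sample", is taken before the 75 g glucose drink. Glucose is then measured at 15, 30, 45, 60, 90 and 120 min. Biochemical Analysis has the glucose samples refrigerated and then "placed in a -20°C freezer until analysis which will be performed within 5 days".

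**Analysis.** The Statistical Analysis section reads: "Incremental areas under the blood glucose, insulin and triglyceride response curves (AUC), ignoring area below fasting, will be calculated". Concentrations and AUCs go into a repeated measures ANOVA, followed by Tukey comparisons of means. OBJECTIVES adds glucose increments at the six times from 15 to 120 min as a secondary objective.

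**Safety.** ADVERSE EVENT REPORTING begins: "An adverse event (AE) is any symptom, injury, illness, or medical/surgical procedure whether planned or not". It does not mention laboratory findings. The Risks section names gastrointestinal symptoms and signs of allergy or infection, but not low glucose. The only glucose limit in the Exclusion criteria, which can also trigger withdrawal, is an upper one.

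**The concern.** If a product enhances insulin signalling and lowers glucose, glucose lower than intended is a plausible extension of that effect. The trial gives 2 g and 4 g to fasting people without diabetes and already measures glucose at the times when a fall could appear. Yet no planned output says how many subjects had a low reading on a given treatment, and nothing asks the study physician to look at the glucose results.

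The primary objective is to find the dose that cuts glucose AUC by at least 33%. The plan could identify such a dose and still be unable to say, from its own outputs, whether any subject had low glucose on it. What is at stake is the safety statement that accompanies the chosen dose. The efficacy estimate is not affected.

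**Working it through.** The documents give no figure for low glucose. Their only power figures concern the AUC difference and do not bear on this point. The check is whether each planned output could reveal an individual low.

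**1. Data available.** There are four Axulin treatments (2 g and 4 g, as capsules and as tablets), two controls (placebo capsules and water alone) and 20 planned completers.
- Axulin test days: 4 × 20 = 80. Control days: 2 × 20 = 40.
- Post-dose readings per Axulin day: the 40 min sample plus six after the drink = 7. Total: 80 × 7 = 560.

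**2. Incremental AUC.** Assume a curve of 5.0, 6.5, 8.0, 7.5, 6.5 and 5.0 mmol/L at 0, 15, 30, 45, 60 and 90 min. By trapezoids above the starting value, the segments are 11.25 + 33.75 + 41.25 + 30.0 + 22.5 = 138.75, or 138.8 mmol·min/L. The last segment adds nothing if the 120 min value is at or below 5.0. These values are illustrations, not proposed limits.

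| 120 min value (assumed) | Incremental AUC | Net AUC |
|---|---|---|
| 5.0 | 138.8 | 138.8 |
| 3.9 | 138.8 | 122.2 |
| 3.0 | 138.8 | 108.8 |
| 2.5 | 138.8 | 101.2 |

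The AUC as defined carries no information about readings below the fasting value.

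**3. Mean concentrations and increments.** Low readings do enter here, and increments can be negative. But one subject 1.5 mmol/L lower (assumed) shifts a mean of 20 by 1.5/20 = 0.075 mmol/L. If 19 subjects average 5.5 at 120 min (assumed), moving the twentieth from 5.0 to 3.0 changes the mean from 5.475 to 5.375. A general shift would show; an isolated low would not.

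**4. The 40 min sample.** It is not among the listed increments, and the plan does not say which times the concentration ANOVA covers. Nor does it say whether this sample or the pre-dose one is the fasting baseline. If the 40 min sample is the baseline, a fall before the drink is absorbed into it. If the pre-dose sample is, any area below that value counts as zero in the AUC.

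**5. Adverse events.** A symptom-free low does not fit the listed terms. The protocol assay, run on frozen samples within 5 days, need not give a result during the visit, and no step sends results to the physician.

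**6. What a count could tell.** With 20 subjects on a treatment, P(at least one low) = 1 − (1 − p)^20. For assumed true rates p of 5%, 10% and 20% this is 64%, 88% and 99%. If none is seen, the one-sided 95% upper bound is 1 − 0.05^(1/20) = 13.9%.

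**The case against.** The strongest case on the other side has five parts.

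- **Low values are not lost.** A reader might infer that they would be reported nowhere. That is too strong: they enter the concentration ANOVA and the time-point increments, so a shift at 90 or 120 min would show by treatment. What is missing is identification and counting by subject.
- **Below fasting is not the same as too low.** A reader might infer that the AUC rule removes exactly the harmful part of the curve. The documents do not support this. The rule drops area below each subject's own fasting value, and subjects with fasting glucose up to 6.9 mmol/L are eligible. The rule is not an error for efficacy.
- **The risk is inferred.** The supporting statements are in vitro and animal, and the human hypothesis is that insulin falls along with glucose. Subjects drink 75 g glucose after the 40 min sample, stay on site to 120 min and are then offered a snack. No figure in the documents supports any rate of lows. All of this stands.
- **Symptomatic lows are caught.** Any symptom or illness is an adverse event, assessed at each visit and evaluated by the study physician. The gap is confined to lows without symptoms after single supervised doses.
- **The values can be tabulated later.** They can, but the tablet block is open label and assays run within 5 days, so a limit chosen later could be chosen with results and some treatments known.

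The silence of the Risks section does not settle the matter. Its reasoning concerns resistant maltodextrins and resistant starch, which are not among this trial's listed treatments.

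**Conclusion.** The point holds as a gap in safety reporting. Individual low glucose readings are neither identified nor counted, and laboratory values lie outside the stated adverse event definition. It does not show that Axulin causes low glucose, that the AUC definition is wrong, or that the efficacy result is at risk.

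The gap covers 560 post-dose readings on 80 Axulin test days, none of which would be examined as a possible low under the plan as written. The conclusion rests on reading the stated mechanism as making low glucose plausible, and on 20 completers. The 1.5 mmol/L shift, the illustrative curve and the true rates are assumptions. The change is worth making before the trial starts, because it uses data already collected and widens what the trial can say about a chosen dose.

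**What to change.** Keep the AUC definition for efficacy, and make two additions.

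- **Statistical Analysis.** Add a descriptive safety table by treatment: the number of subjects with any post-dose glucose below a prespecified limit, with an exact confidence interval; each subject's lowest post-dose glucose; and the change from the pre-dose fasting sample to the 40 min sample. Set each Axulin treatment against the control in its own block (placebo capsules or water alone). The investigator and sponsor should choose the limit and fix it before the first test visit. Fixing it only before unblinding is not enough, because the tablet block is open label.
- **ADVERSE EVENT REPORTING.** Extend the definition to laboratory values that the study physician judges clinically significant, and state that glucose results go to the physician when assayed. Without the second part, the first has nothing to act on.

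The cost is one table, one clause and a brief review of results, with no new samples or visits. Any value judged clinically significant would also fall under the existing rule that all adverse events are reported to Health Canada. With 20 subjects per treatment the table cannot show that a dose is free of the harm, and the report should say so.
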